## **4.2 Exclusion Criteria**

The presence of any of the following will exclude a subject from study enrollment:

- 4.2.1 Any prior treatment with azacitidine or decitabine.
- 4.2.2 Patients diagnosed with APL, AML-M3.
- 4.2.3 Patients receiving other active treatment for their myeloid malignancy including investigational agents with the exception of hydrea for WBC control.
- 4.2.4 Nursing or pregnant women.
- 4.2.5 History of allergic reactions to either azacitidine or ascorbic acid.
- 4.2.6 Patients with uncontrolled intercurrent illness including, but not limited to ongoing or active infection, symptomatic congestive heart failure, unstable angina pectoris, cardiac arrhythmia, or psychiatric illness/social situations that would limit compliance with study requirements.

4.2.7 Patients with higher risk of bleeding (deemed by the treating physician) or on anticoagulation.

4.2.8 Patients who are unwilling or unable to comply with all study requirements.

#### **4.3 Inclusion of Women and Minorities**

Men, women and members of all races and ethnic groups are eligible and encouraged to participate in this trial.

#### **5.0 Registration**

All subjects who have been consented are to be registered in the OnCore™ Database. For those subjects who are consented, but not enrolled, the reason for exclusion be recorded.

All subjects will be registered through Cleveland Clinic and will be provided a study number by contacting the study coordinator once the patient signs the consent.

#### **6.0 Treatment Plan**

##### **6.1 Treatment Regimen Overview**

All azacitidine courses will be given at Cleveland Clinic Taussig Cancer Institute or an affiliate hospital approved to treat patients.

###### **6.1.1 Azacitidine**

Azacitidine will be administered intravenously or subcutaneously at a fixed dose of 75mg/m^2/day for 7 consecutive days, allowing interruptions for weekends and holidays within each 28-day cycle. No dose modifications will be permitted during the treatment period.

#### **6.1.2 Ascorbic Acid**

Ascorbic acid will be administered orally daily at 1 g/day three days prior to start azacitidine and then continues daily for a total of 28 days of each 28 day cycle. No dose modifications will be permitted during the treatment period.

### **6.2 Treatment Duration**

The length of the treatment will vary per patient. The typical treatment period will be 6 months for the course of the required treatment. If the patient is eligible to continue treatment during the ETP, the patient is able to receive treatment until the patient meets one or more of the EOT criteria.

### **6.3 General Concomitant Medications and Supportive Care Guidelines**

Patients should be off any prior treatment or line of therapy for 2 weeks prior to start study with the exception of hydrea.

Necessary supportive measures for optimal medical care will be given throughout the treatment as determined by the treating physician and the patient's medical need. No concomitant chemotherapy, immunotherapy, or therapy with monoclonal antibodies will be allowed during the study with the exception of hydroxyurea or corticosteroids for control of blood counts.

Use of a colony-stimulating factor or combinations thereof (e.g. G-CSF, GM-CSF, or erythropoietin) are at the discretion of the treating physician and is permitted if judged in the patient's best medical interest.

Prophylactic antibiotics, antifungals, and antiviral agents (e.g. levofloxacin, itraconazole, valacyclovir, etc.) are recommended; however, the use of these or other drugs will be left to the treating physician's discretion.

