#### **4.1 Subject Selection**

#### **4.2 Inclusion Criteria**

Subjects must meet all of the following inclusion criteria to be eligible for enrollment:

4.2.1 Patients must have a confirmed *TET2* mutations identified by next generation targeted deep sequencing.

4.2.2 Patients must have MDS, or MDS/MPN overlap defined by 2016 WHO criteria. Both newly diagnosed or previously treated MDS or MDS/MPN patients are eligible as long as the patient has never received prior treatment with azacitidine or decitabine.

4.2.3 Patients with Leukemic/blast phase transformation MPN.

4.2.4 Patient with AML according to 2016 WHO criteria (excluding APL [AML-M3]).

4.2.4.1 Newly diagnosed patients who are ineligible or declined to receive intensive chemotherapy after discussion of risks and benefits of that approach or patients with primary refractory/relapsed AML.

4.2.4.2 Patients with active central nervous system (CNS) leukemia eligible at the discretion of treating physician.

4.2.4.3 Relapse/Refractory is defined as at least 1 course of treatment for AML excluding any patients treated with azacitidine or decitabine.

4.2.4.3.1 Patients should be off any prior treatment or line of therapy for 2 weeks prior to start study with the exception of hydrea (Hydroxyurea).

4.2.5 Prior therapy with hydroxyurea, biological or targeted therapy (e.g. flt3 inhibitors, other kinase inhibitors) or hematopoietic growth factors is allowed.

4.2.6 Age  $\geq 18$  years.

4.2.7 ECOG performance status  $\leq 3$ .

4.2.8 Patients must have normal organ and marrow function as defined at the discretion of the treating physician and PI.

- 4.2.9 Women of childbearing potential must have a negative serum or urine pregnancy test within 10-14 days prior to enrollment.
- 4.2.10 Patients must have the ability to understand and the willingness to sign a written informed consent document.
- 4.2.11 Patient must be willing to comply with all aspects of the protocol including completing the drug diary.
- 4.2.12 Patient must discontinue any and all use of multivitamin and/or vitamin c medication 24 hours before first dose of Ascorbic Acid.

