#### **Treatment Period (Day -3 to C6D28)**

1. Hematology exams (Appendix VI) at the start of each cycle (day 1) and the last day of cycle 6 (C6D28)
2. Serum Chemistry (Appendix VI), including Creatinine, bilirubin, ALT or AST at the start of each cycle (day 1)
3. Bone marrow aspirate and/or biopsy to confirm response, to be performed at the end of cycle 6. 10 ML of whole blood or bone marrow aspirate whichever available will be collected in extra lab tube. All bone marrows samples are to be stored at Cleveland Clinic
4. Conventional cytogenetics to be performed at the end of cycle 6
5. Documentation of frequency of transfusions (only PRBC and Platelets) prior to start of each new cycle.
6. Documentation in the medical record of any grade 2 or higher adverse events at each visit. For guidelines on SAE Reporting and AE entry for Case Report
7. Documentation of any prior administration of growth factors and ESA prior to start of each cycle
8. A 10 ML blood sample that will be used for next generation targeted deep sequencing of genes that are common in myeloid malignancies

9. Physical exam and ECOG performance status occurring at the end of each cycle
10. Vital signs occulting at each visit
11. Pregnancy test if applicable
12. MDS Response Assessment, assessed by the treating physician occurring at the end of cycle 6 or EOT, whichever occurs first.
13. Methylation panel only occurring in Cycle 1
14. Azacitidine will be administered intravenously or subcutaneously at a fixed dose of 75mg/m^2/day for 7 consecutive days, (allowing interruptions for weekends, and holidays, of each 28-day cycle).
15. Ascorbic acid will be administered orally daily at 1 g/day three days prior to start azacitidine and then continues daily for a total of 28 days of each 28 days cycle.

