### **Definitions:**

#### **Responses for MDS patients:**

**Complete Response (CR):** Bone marrow:  $\leq 5\%$  myeloblasts with normal maturation of all cell lines; persistent dysplasia will be noted. Peripheral blood:  $\text{Hgb} \geq 11 \text{ g/dL}$   $\text{Platelets} \geq 100 \times 10^9 / \text{L}$   $\text{Neutrophils} \geq 1.0 \times 10^9 / \text{L}$ ,  $\text{Blasts} 0\%$

**Partial response (PR):** All CR criteria if abnormal before treatment except: bone marrow blasts decreased by  $\geq 50\%$  over pretreatment but still  $> 5\%$

**Marrow CR:** Blasts  $\leq 5\%$  and decrease by  $\geq 50\%$  from baseline (baseline blasts should be above 5% to be eligible for marrow CR)

**Hematologic Improvement (HI):** (responses must last at least 8 weeks) **Erythroid response** [HI-E; (if pretreatment  $\text{Hgb} < 11 \text{ g/dL}$ )]:  $\text{Hgb}$  increase by  $\geq 1.5 \text{ g/dL}$ ; Relevant reduction of units of RBC transfusions by an absolute number of at least 4 RBC transfusions/8 weeks compared with the pretreatment transfusion number in the previous 8 weeks. Only RBC transfusions given for an  $\text{Hgb}$  of  $\leq 9.0 \text{ g/dL}$  pretreatment will count in the RBC transfusion response evaluation.

**Platelet response** [HI-P; ((if pretreatment Platelet count  $< 100 \times 10^9 / \text{L}$ )]: Absolute increase of  $\geq 30 \times 10^9 / \text{L}$  for patients starting with  $> 20 \times 10^9 / \text{L}$  platelets, or increase from  $< 20 \times 10^9 / \text{L}$  to  $> 20 \times 10^9 / \text{L}$  and by at least 100%.

**Neutrophil response** [HI-N; (pretreatment,  $\text{ANC} < 1.0 \times 10^9 / \text{L}$ )]: At least 100% increase and an absolute increase  $> 0.5 \times 10^9 / \text{L}$

**Progression/Relapse after hematological improvement:**  $\geq 1$  of the following:  $\geq 50\%$  decrement from maximum response levels in granulocytes or platelets;  $\downarrow$  in Hgb by  $\geq 1.5$  g/dL; transfusion dependence

**Stable Disease:** Not satisfying criteria for Complete Remission, Partial Response, Marrow CR, Hematologic Improvement or Progression/Relapse.

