### **14.0 STATISTICAL CONSIDERATIONS**

**Definition of primary outcome/endpoint:** A binary indicator of overall response, defined as achieving CR, PR, or HI) per 2006 IWG criteria for MDS and MDS/MPN overlap and (CR, CRp, CRi, or PR) per 2003 IWG criteria for AML after 6 cycles of treatment

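### Hematologic improvement alone counts as a primary response in MDS and MDS/MPN, but no scoring rule covers growth factors, so a sustained growth-factor effect can be counted as a response

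*Combined protocol and SAP*

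**What the plan says.** Section 14.0 defines the primary endpoint for MDS and MDS/MPN as "achieving CR, PR, or HI) per 2006 IWG criteria for MDS and MDS/MPN overlap", so HI alone makes a patient a responder. For AML the list is "CR, CRp, CRi, or PR) per 2003 IWG criteria for AML after 6 cycles of treatment", and HI is not on it.

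Section 12.0 sets out HI for MDS. It must last at least 8 weeks.

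- **Erythroid HI** applies to patients with pretreatment hemoglobin below 11 g/dL. It needs a rise of at least 1.5 g/dL; a cut of at least 4 red-cell transfusions per 8 weeks is also listed.
- **Neutrophil HI** applies to patients with pretreatment ANC below 1.0 × 10⁹/L. It needs "At least 100% increase and an absolute increase" of more than 0.5 × 10⁹/L.

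Neither definition mentions growth factors. Nor do the hemoglobin and neutrophil thresholds for CR, which PR shares.

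On use of these agents, Section 6.3 states: "Use of a colony-stimulating factor or combinations thereof (e.g. G-CSF, GM-CSF, or erythropoietin) are at the discretion of the treating physician". It adds that such use "is permitted if judged in the patient's best medical interest". The inclusion criteria say that prior therapy with "hematopoietic growth factors is allowed". Section 11.1 (Treatment Period) calls for "Documentation of any prior administration of growth factors and ESA prior to start of each cycle". Neither Section 12.0 nor Section 14.0 says what that record does to the scoring of response.

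**The concern.** Erythropoietin and G-CSF act on hemoglobin and neutrophils, the values that erythroid and neutrophil HI measure. A patient who meets the threshold because an ESA was started and kept up would satisfy Section 12.0 as written and enter the overall response rate (ORR) as a response to azacitidine plus ascorbic acid.

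The trial is single-arm and tests against a fixed null of 0.30, so no concurrent group would show the same growth-factor effect and cancel it. The treating physician assesses response (Section 11.1) and also decides on growth-factor use (Section 6.3). No planned sensitivity analysis would reveal how many responses were reached on a growth factor. With 28 patients and a cut-off on the response count, one or two misscored patients can change the trial's conclusion.

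**Working it through.** **Inputs from Section 14.0.** Null rate 0.30 and alternative 0.50, one-sided. Stage 1 has 12 patients and stops at 3 or fewer responses. Stage 2 adds 16, for 28 in total. The null is rejected at 11 or more responses. Stated type I error is 0.1 and power 0.8.

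**Formula.** With final boundary r and response probability p,

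P(reject) = Σ over x = 4 to 12 of P[Bin(12, p) = x] × P[Bin(16, p) ≥ r − x].

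**The plan's own figures first.**

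| Final boundary | Type I error (p = 0.30) | Power (p = 0.50) |
|---|---|---|
| 11 or more (as written) | 0.169 | 0.868 |
| 12 or more | 0.095 | 0.802 |

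The stated 0.1 and 0.8 match a boundary of 12, not the written 11. That mismatch is a separate matter. It is shown here because each figure below needs its own baseline: 0.169 for a boundary of 11 and 0.095 for 12.

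**Assumption.** The documents give no rate of growth-factor use and no rate of misscoring. Let x be the share of susceptible true non-responders scored as HI only because of a growth factor, and s the share of non-responders who are susceptible, that is, who have MDS or MDS/MPN. With a true ORR of 0.30, the apparent ORR is 0.30 + 0.70 × s × x.

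**Case A: all non-responders susceptible (s = 1).**

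| x | Apparent ORR | P(reject), 11 or more (baseline 0.169) | P(reject), 12 or more (baseline 0.095) |
|---|---|---|---|
| 3% | 0.30 + 0.70 × 0.03 = 0.321 | 0.24 | 0.14 |
| 5% | 0.30 + 0.70 × 0.05 = 0.335 | 0.29 | 0.18 |
| 10% | 0.30 + 0.70 × 0.10 = 0.370 | 0.43 | 0.30 |

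**Case B: half the non-responders have AML (s = 0.5).**

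| x | Apparent ORR | P(reject), 11 or more (baseline 0.169) | P(reject), 12 or more (baseline 0.095) |
|---|---|---|---|
| 3% | 0.30 + 0.35 × 0.03 = 0.3105 | 0.20 | 0.12 |
| 5% | 0.30 + 0.35 × 0.05 = 0.3175 | 0.22 | 0.13 |
| 10% | 0.30 + 0.35 × 0.10 = 0.335 | 0.29 | 0.18 |

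**In patients.** At a true ORR of 0.30, the expected number of non-responders among 28 is 28 × 0.70 = 19.6. In Case A, x = 5% is 0.05 × 19.6 ≈ 1 patient. That one patient takes the false-positive rate from 0.169 to 0.29 under a boundary of 11, or from 0.095 to 0.18 under 12.

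**The case against.** The strongest reply is that the endpoint already has protection.

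- **Durability.** HI must last at least 8 weeks. This stands: a short neutrophil rise after brief G-CSF is not HI. It does not exclude sustained G-CSF or a continuing ESA.
- **Who is exposed.** Only MDS and MDS/MPN patients with low pretreatment hemoglobin or ANC can be affected. HI is not a response in AML, where CRi counts even with ANC below 1.0 × 10⁹/L. This stands, and it is why Case B is given. The plan fixes no AML share.
- **Clinical restraint.** Use must be judged to serve the patient, and the local PI signs off responses at cycle 6. Both are true, but neither tells the signatory how to score a rise that occurred on a growth factor.
- **The cited criteria.** Sections 12.0 and 14.0 refer to IWG 2006. Whether that source has its own growth-factor rule cannot be checked from these documents. The definitions that Section 12.0 writes out contain none.
- **The null.** If the experience behind the 0.30 was scored just as permissively, part of the effect is already in the null and the net bias is smaller. The documents do not say.

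A reader might infer that any count rise on G-CSF becomes a response. The 8-week requirement rules that out. A reader might also set 0.24, 0.29 and 0.43 against the stated 0.10. That would charge the boundary mismatch to growth factors; the right comparison is 0.169.

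**Conclusion.** The concern holds as a gap in the endpoint definition for MDS and MDS/MPN. Followed as written, the plan can count a sustained growth-factor or ESA effect as HI, and so as a primary response. The documents do not show that this will happen often, and they do not support calling the ORR biased by any particular amount.

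The false-positive rates are illustrations. They rest on an assumed misscoring share of 3% to 10% and on the AML share. Across those assumptions, the rise is from 0.169 to between 0.20 and 0.43 with the written boundary, and from 0.095 to between 0.12 and 0.30 with a boundary of 12. The point stands under either boundary. It should be fixed, because very few patients can matter and the rule is easy to write.

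**What to change.** Change the scoring only; supportive care stays as it is.

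1. Add to Section 12.0: neutrophil HI is not credited on counts taken during G-CSF or GM-CSF use; erythroid HI is not credited while the patient is on an ESA that was started or increased after baseline, whenever it was started. The last clause matters because an ESA begun in cycle 1 and continued would escape a rule that looked only at starts within the 8-week window.
2. Leave CR and PR in the primary analysis as written. Withholding the neutrophil part of CR could turn an MDS patient with genuine blast clearance into a non-responder, since marrow CR is not a primary response in Section 14.0.
3. Add two sensitivity analyses of ORR to Section 14.0: one without the rule in item 1, and one that applies it and also counts as non-response any CR or PR whose blood-count criteria were met only on a growth factor.
4. Set the rule before responses are adjudicated.

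**Cost.** ORR may be slightly lower. Section 11.1 already asks for growth-factor and ESA use to be documented before each cycle, but it does not clearly require dates or doses. The record must capture start and stop dates and ESA dose increases.

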#### **6.4 Criteria for Removal from Study Treatment (EOT)**

In the absence of treatment delays due to adverse events, treatment may continue for 6 cycles or be extended after 6 cycles unless 1 one of the following criteria applies:

End of Treatment Criteria

• Disease progression defined as no response after 6 months of treatment or loss of response during treatment as defined in section 12

• Intercurrent illness that prevents further administration of treatment

• The investigator and/or treating physician considers it to be in the best interest of the subject to permanently discontinue study treatment

○ This includes if the treatment is deemed to be of excessive toxicity to the patient by the treating physician

• Patient decision to withdraw from treatment (partial consent) or from the study (full consent)

• Pregnancy during the course of the study for a child-bearing participant

• Death

• Unacceptable adverse events defined as following:

○ Unacceptable treatment related toxicity, NCI CTC AE version 4.0 Grade 3 or 4 that fails to recover to baseline or < Grade 3 in the absence of treatment within 4 weeks

○ Any toxicity or other issue that causes a delay of study drug administration by more than 4 weeks

Table 1: End of Treatment Criteria

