#### **3.2 Expected Duration of Treatment and Subject Participation**

Upon signing consent, patients will be enrolled onto the study. Patients will undergo a screening period. The screening period is defined as the time period between the signing of the consent to the day the patient receives the first dose of study drug. During this period the patient will be assessed to determine if the patient meets all inclusion and exclusion criteria to be eligible for the study (Appendix IV).

The treatment period is defined as the time between first day of study drug dosage (Day - 3) to C6D28. At this time the patient will be assessed and eligible to move into the Extended Treatment Period (ETP). The extended treatment period is defined as C7D1 to the patient meets EOT criteria (Section 6: Table 1; Appendix IV)

Study treatment is defined as the treatment period and if applicable the extended treatment period (Appendix IV). Study drug will be continued during the duration of the study treatment unless patients exhibit any EOT criteria (Section 6: Table 1; Appendix IV).

Treatment should be continued for at least 6 cycles in the absence of toxicities that require discontinuation and/or any EOT criteria (Section 6: Table 1; Appendix IV). After 6 cycles of treatment, a bone marrow biopsy and aspiration will be obtained to evaluate response. If patient has achieved either of the below response criteria (Appendix IV) based on their disease diagnosis patient will be eligible continue onto the extended treatment period (ETP). The patient is eligible to remain on treatment during the ETP until disease progression or patient meets EOT criteria (Section 6: Table 1; Appendix IV).

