#### Response Criteria for extended treatment eligibility

- complete remission, partial remission, or hematologic improvement (CR/PR/HI) per IWG 2006 criteria for patients with MDS
- (CR/PR/marrow CR) per IWG 2003 criteria for patients with AML
- If the response is stable disease and the investigator determines the patient is gaining clinical benefit, patient may continue on treatment until progression.

At the point in which the patient meets the any EOT criteria (Section 6) the patient will enter into the follow up period to follow for survival status. The patient will be followed for up to 1 year and/or death, whichever were to occur first. End of study (EOS) is defined as the time the patient completes 1 year of survival follow up and/or patient's death, whichever were to occur first.

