**Definition of secondary outcomes/endpoints:**

1. Incidence of adverse events of the combination defined by CTCAE 4.1 criteria.  
Toxicity will be any drug related Grade 3 or 4 toxicity.
2. Response duration to the combination recorded from start of treatment to progression
3. Overall survival measured from start of treatment to death or last follow up

**Sample size justification and study design:** The study sample size was determined using Minimax Simon's two-stage design (Simon, 1989. The null hypothesis that the true response rate is 0.3 will be tested against a one-sided alternative that the true response rate is 0.5. In the first stage, 12 patients will be accrued. If there are 3 or fewer responses, the study will be stopped. Otherwise, 16 additional patients will be accrued for a total of 28. The null hypothesis will be

rejected if 11 or more responses are observed in 28 patients. This design yields a type I error rate of 0.1 and a power of 0.8 when the true response rate is 0.5.

**Analysis plan:** Descriptive statistics will be used for the primary endpoint and secondary endpoints 1,2, and 3. Overall survival will be estimated with Kaplan Meier method and will be compared to the survival of a historical cohort of MDS patients treated at our institution with single agent Azacitidine between 2006-2012 using a one-sample log rank test. A Cochran-Mantel-Haenszel test will be used to test for differences in response rate by mutational status controlling for treatment. Unadjusted and adjusted logistic regression models were used to predict response to therapy. Models will be adjusted for covariates including age, sex, and other prognostic factors. The odds ratio (OR) and 95% confidence intervals (CI) will be estimated for the risk group (mutated) and compared with the reference group (WT).

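### Table 1 labels stable disease at month 6 as progression while Section 3.2 and Appendix V let it continue, and Section 12 lacks the progression rules that response duration needs

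*Combined protocol and SAP*

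**What the plan says.** Four places in the protocol bear on this.

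- **Section 6.4, Table 1** lists the end-of-treatment (EOT) criteria. The first is "Disease progression defined as no response after 6 months of treatment or loss of response during treatment as defined in section 12". One criterion is enough: "treatment may continue for 6 cycles or be extended after 6 cycles unless 1 one of the following criteria applies".
- **Section 3.2 and Appendix V**, on eligibility for the extended treatment period (ETP), say: "If the response is stable disease and the investigator determines the patient is gaining clinical benefit, patient may continue on treatment until progression". Section 3.2 also limits that period: "The patient is eligible to remain on treatment during the ETP until disease progression or patient meets EOT criteria".
- **Section 12** defines stable disease, in the MDS list, as "Not satisfying criteria for Complete Remission, Partial Response, Marrow CR, Hematologic Improvement or Progression/Relapse". Its only progression entry is headed "Progression/Relapse after hematological improvement" and rests on falls in granulocytes, platelets or hemoglobin, or on transfusion dependence. The AML list has CR, CRi, CRp and PR, and no entry for stable disease, relapse or progression.
- **Section 14** gives secondary endpoint 2 as "Response duration to the combination recorded from start of treatment to progression" and names no analysis population. Secondary endpoint 3 is "Overall survival measured from start of treatment to death or last follow up".

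**The concern.** Two faults meet here.

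First, a rule for ending treatment has been written as a definition of progression. It gives the progression label to patients whom Section 12 would call stable and whom Section 3.2 may keep on treatment.

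Second, the section that Table 1 cites for loss of response covers only one of the situations in which response can be lost.

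At stake is the event for response duration. With no population named and the clock starting at the beginning of treatment, two analysts could date the same patient differently, or find no written event for a CR or AML responder who relapses. In an open-label trial of 28 patients, settling those rules after outcomes are known would invite bias. The EOT date matters as well, because survival follow-up is counted from it.

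**Working it through.** The documents give no figure to reproduce on this point, so the check is a reading of the sections against each other, followed by a scale.

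**Step 1. One MDS patient, stable at the end of cycle 6, judged by the investigator to benefit.**

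| Place | Status of this patient |
|---|---|
| Table 1 | No response after 6 months, so progressed; EOT criterion met |
| Section 3.2 and Appendix V | May continue until progression |
| Section 3.2, limit on the ETP | Must leave on progression or any EOT criterion, which leads back to Table 1 |
| Section 12 | Stable, which by definition is not progression |

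The patient meets a criterion for leaving the extended period on the day of entering it. The rows cannot all hold.

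**Step 2. The reference from Table 1 to Section 12.**

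| Situation | Progression or relapse rule printed in Section 12 |
|---|---|
| MDS, after hematologic improvement | Yes |
| MDS, after CR or PR | None |
| MDS, never responded | None |
| AML, any | None |

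The stable patient in Step 1 falls in the third or fourth row. So the event that would end continued treatment under Section 3.2 is itself unwritten.

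**Step 3. Which endpoints use progression.**

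- Primary endpoint: binary response after 6 cycles. It does not use progression. The evaluability sentence in Section 12 mentions clear progression, but for patients with fewer than 2 courses, whom a 6-month rule cannot reach.
- Response duration: progression is its event. If only responders are analysed, the non-response part of Table 1 does not apply, but the gaps in Step 2 do. If all treated patients are analysed, a stable patient has an event at about month 6 under Table 1, or a later one under Section 3.2.
- Overall survival: not defined by progression. Follow-up runs one year from EOT (Section 6.5, calendar note K, Appendix IV). EOT at month 6 gives 6 + 12 = month 18 as the end of follow-up; continued treatment moves it later by the same amount.

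**Step 4. Scale.** Inputs from Section 14: N = 28, response rates 0.5 and 0.3.

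- Expected non-responders: 28 × (1 − 0.5) = 14, and 28 × (1 − 0.3) = 19.6.
- These counts include patients who died, withdrew or stopped earlier and so had already met another EOT criterion. They also assume full enrolment. At a true rate of 0.3, the chance of 3 or fewer responses in the first 12 is the sum over x = 0 to 3 of C(12, x) × 0.3^x × 0.7^(12 − x) = 0.49, so the trial would stop at 12 about half the time.
- The conflict affects only non-responders still on treatment with stable disease and judged benefit. The documents give no share. Purely as an illustration, an assumed share of 20% to 60% gives 0.2 × 14 = 2.8 to 0.6 × 19.6 = 11.8, or about 3 to 12 patients.

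**The case against.** **Stable disease might count as a response.** Section 12 lists it under the heading for MDS responses, and Section 3.2 speaks of the response being stable disease, so Table 1's non-response could be read to exclude it. This does not survive Section 14, which counts only CR, PR or HI for MDS and MDS/MPN, or Section 12, which defines stable disease as meeting none of the response categories.

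**Section 3.2 might simply be the specific rule that overrides Table 1.** A site could work that way, but nothing says so, and Section 3.2 itself makes the extended period subject to the EOT criteria.

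**The plan names the IWG 2006 and 2003 criteria, which may supply the missing definitions.** This stands in part. Their content cannot be checked from the documents. Table 1, however, sends the reader to Section 12, and Section 12 prints a single rule.

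**Response duration implies responders.** This also stands: under that reading the month-6 conflict does not reach the endpoint. Section 14 does not state it, and the gaps for CR, PR and AML remain.

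**Readings that go too far.** A reader might infer that progression-based endpoints in general are undefined. Only response duration is timed to progression, and for stable patients the result is conflicting dates rather than no date. A reader might also infer that all 14 to 20 non-responders are affected; continuation requires stable disease and judged benefit, so it is a subset. Finally, a reader might infer a biased survival estimate. The documents show only that follow-up length depends on the EOT date. It varies between patients under either rule, and no bias in the Kaplan-Meier estimate has been shown.

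**Conclusion.** The contradiction is real and in current text. A patient with stable disease and investigator-judged benefit after cycle 6 is progressed under Table 1, not progressed under Section 12, and eligible to continue under Section 3.2 and Appendix V. How many patients this concerns cannot be derived from the documents; the 3 to 12 above rests wholly on an assumed share.

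Separately, Section 12 has no rule for loss of CR or PR in MDS, for progression in patients who never responded, or for AML.

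The consequence is confined to response duration, plus the date on which survival follow-up ends. Response duration has conflicting event dates for stable patients if all treated patients are analysed, and no written event rule for CR, PR or AML responders under either population. The primary endpoint is untouched. This should be corrected before response duration is analysed.

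**What to change.** 1. Reconcile Section 3.2, Section 6.4 (Table 1) and Appendix V on stable disease after cycle 6. Which treatment rule applies is for the investigators; this review takes no side.
2. Whatever is decided there, state that for endpoint dating, non-response at month 6 is not by itself a progression event.
3. State in Section 14 that response duration is analysed in responders.
4. Add to Section 12 the progression or relapse definitions for MDS after CR or PR, for patients who never responded, and for AML. Take them from the response criteria the plan already names and apply them to the assessments already scheduled.

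The cost is wording in Sections 3.2, 6.4, 12 and 14 and Appendix V, with no added visits. There is one small downside. Marrow is scheduled at screening and the end of cycle 6, is optional at EOT, and is not listed for extended treatment. Marrow relapse in that period would be dated only when a clinically driven or optional EOT marrow is done. That should be stated as a limitation of response duration.
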